B. *Wide variations in disparity highlight uncertainty.* Careful literature review documents that disparities in health services related to disability are complex and sometimes not consistent. Although PWD consistently receive fewer preventive services such as dental care, mammograms, or fecal occult blood tests compared to PWOD with the same chronic conditions, practice patterns vary. Our preliminary studies found that people with mild disabilities were more likely to receive influenza vaccines than PWOD, while those with the most severe disabilities experiencing the greatest need and the greatest access barriers were less likely vaccinated. These inconsistencies may relate to greater medical needs interacting with hampered abilities to obtain services.

C. *Policy change can benefit populations.* Potentially preventable hospitalizations for certain conditions are declining in the general population suggesting improvements in ambulatory care. Greater access to community health centers, rural health clinics, Medicaid Managed Care, Health Maintenance Organizations, and implementation of Medicare Part D with increased drug coverage have been linked to reduced hospitalizations. Having a regular place of care is associated with receipt of better prevention. This suggests that policies supporting greater access to ambulatory care may be improving population health. If access disparities are severe among PWD, that sub-population may be excluded from these benefits.

D. *Importance to patients or caregivers:* The Institute of Medicine's (IOM) September 2012 report, "Best Care at Lower Cost," calls for improving "capacity to capture clinical, care delivery processes" and achieving "better care, system improvement and the generation of new knowledge." PWD, family members, and healthcare providers partnering with researchers who will analyze a decade of records from the ongoing Medicare Current Beneficiary Survey (MCBS) about clinical and care delivery processes will be partnering to develop the ecologically valid **Patient-Informed Surveillance Tool.** This Tool will have the potential to improve the

PRINCIPAL INVESTIGATOR (LAST, FIRST, MIDDLE): [name]

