#### ***Selection Criteria for CBPR and Qualitative Study***

Each VAI and Urban group will include 4 to 6 PWD, 1 or 2 PWOD, and 1 or 2 caregivers. Clinician groups will be separate and will also consist of about 6 to 8 individuals per group. PWD will be defined as being at ADL- and/or IADL-I, II, III, or IV, and PWOD as being at ADL- and IADL-0. Clinicians must be clinically active health professionals (nurse, physician, physical therapist, and others). Inclusion criteria are: 1) Age 21 years old or older and living in a US community; and 2) The ability to communicate and participate in small group dialogue online (VAI groups) or in-person (Urban groups) with or without an Americans with Disability Act (ADA) accommodation.

Sampling will be purposive to ensure enrollment of people from diverse socioeconomic circumstances and across the broad spectrum of disability type and severity. Participants for the VAI groups will be recruited through the VAI membership of over 700 PWD and 175 caregivers of PWD, building on protocols established and applied extensively in Second Life by our

PRINCIPAL INVESTIGATOR (LAST, FIRST, MIDDLE): [name]

consultant [name]. Participants in the Urban groups will be recruited from JFS Housing, Inc. (with about 135 PWD) through community newsletters and community meetings. Clinicians will be recruited through Second Life. The stakeholder consultant ([name]) personally has about 100 medical professional contacts within Second Life including nurses, paramedics, physicians, midwives, occupational therapists, and mental health counselors belonging to over 60 Second Life health professional groups.

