**Aim 2** will address the degree to which people with disabilities experience healthcare disparities. The comparators will be the outcome here and ADL/IADL stages will be the main exposure. We will model each trichotomously expressed comparator through multinomial logistic regression. We will report adjusted relative risk ratios (RRRs) and their 95% confidence intervals (CIs) for the ADL and IADL stages (stage I as reference). For each continuously expressed comparator, we will report sample weighted estimates for the ADL and IADL stages (stage I as reference) obtained through linear regression.

**Aim 3** will determine if people who experience better access and higher quality healthcare and who rate their PCPs highly on technical skills, inter-personal manner, and the provision of sufficient information to understand their health condition(s) will be less likely to experience a negative transition outcome. The 5-state transition outcome will be modeled by multinomial logistic regression models with no change in function as reference. We will report RRRs and their 95% CIs. In the multinomial logistic regression, the relative risk of improvement in function, decline in function, institutionalization, or death will be defined as the probability of improvement in function, decline in function, institutionalization, or death divided by the probability of remaining at the same ADL stage.

Each of the 5 comparators will be modeled individually after considering other covariates. They will also be entered into one model to determine the relative independent effects of each after considering the other exposures.

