#### Sample size

We did power calculation for Aims 2 and 3. Here, we focus on the association between ADL stage and the first comparator, care coordination and quality, in Aim 2, and that between the first comparator and transition in Aim 3.

First, we show the detectable RRRs for associations between ADL stages and the first comparator. Using our preliminary data in Table 2 which included three panels, we assume the distribution of the ADL stages will be similar across 10 years for which we will request the data for the project. After trichotomizing the first comparator, we obtained the proportion for the three categories (1, 2, and 3 from dissatisfied to satisfied) for stage I. They are 13.32%, 60.19%, and 26.49%.

Relative risk of being dissatisfied is defined as the probability of being dissatisfied divided by the probability of being neither dissatisfied nor satisfied. The detectable RRRs comparing other stages to stage I are shown in Table 3. With 10 years of data, we will be able to detect RRRs of 0.91 and 1.07 when comparing stages 0 to I. The RRRs we observed using 1 year data are actually much bigger than these, which indicate that we have adequate power.

Table 3. Detectable RRRs comparing other Stages to Stage I (assuming 80% power and 5% significance level)

	Category 1 versus Category 2	Category 3 versus Category 2
Stage 0 versus I	0.91	1.07
Stage II versus I	1.15	0.89
Stage III versus I	1.16	0.88
Stage IV versus I	1.29	0.80

We then calculate the detectable RRRs when we compare the transition outcome across the three groups for the first comparator. We again assume the distribution of the first comparator will be similar across 10 years and the transition probability for the reference category, "neither dissatisfied nor satisfied," was estimated from the 1 year transition in ADL stages for the three panels that were active in both 2005 and 2006. Relative risk of functional improvement is defined as the probability of ADL functional improvement divided by the probability of being stable in ADL stage. All the detectable risk ratios (Table 4) are smaller than 2 except for one RRR for institutionalization, which indicate ample power for our analysis.

Table 4. Detectable RRRs of transition (functional stable is the reference) for the three categories of the first comparator (assuming 80% power and 5% significance level)

	Death	Institutionalization	Functional deterioration	Functional improvement

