Dissatisfied vs. neither dissatisfied nor satisfied	1.71	2.71	1.50	1.49
Satisfied vs. neither dissatisfied nor satisfied	1.24	1.63	1.16	0.90

Qualitative: The SL group analyses will include geographically diverse stakeholders with a variety of socioeconomic circumstances, disabilities, comorbidities, and life circumstances. The SL groups will be computer literate. The addition of Urban groups further enriches the sample

PRINCIPAL INVESTIGATOR (LAST, FIRST, MIDDLE): [name]

by obtaining PWD from a predominantly minority low literacy population. The SL and Urban recruitment strategies enable the inclusion of hard-to-reach people, including those who face numerous disability-related, economic, educational, social class, ethnicity, and cultural barriers.

By design, the MCBS samples are weighted to be representative of the entire elderly and working age Medicare population, and thus by its nature will include a diverse study population. The sample will also have a wide range of medical comorbidities. Preliminary results (Table 5) show diversity with respect to ADL and IADL stage as well as transition outcome status (above). Finally, the sampling frame is designed to be geographically diverse. Table 5 provides sample size estimates from 3 active panels of respondents at the fall 2006 Access to Care interview (about 3/10ths the study sample size). Over 4 and 5 million people had mild ADL or IADL limitations, respectively, with another 4.6 and 7.0 million people having more serious ADL and IADL limitations. Between-group differences across the 5 comparators will be addressed quantitatively according to the transition outcomes with independent effects of ADL and IADL stage determined.

Table 5. Sample size shown for 3 panels; expected size for 10 panels will be 40,000

Stage	Difficulties in ADL			Difficulties in IADL		
	Raw N	Expected N in population (million)	Weighted percent (SE on weighted %)	Raw N	Expected n in population (million)	Weighted percent (SE on weighted %)
0	8208	21.1	69.25 (0.86)	6924	18.2	59.65 (0.97)
I	1942	4.8	15.73 (0.50)	2094	5.3	17.5 (0.59)
II	995	2.4	7.72 (0.37)	1141	2.9	9.45 (0.37)
II	728	1.8	5.97 (0.36)	1558	3.4	11.1 (0.41)
IV	185	0.4	1.33 (0.14)	341	0.7	2.3 (0.15)
Total	12058	30.5	100	12058	30.5	100

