**Quantitative: Overview and General Approach to Multivariable Estimation:** Our specific aims focus on empirically quantifying disparities in the quality of health and PCP care as perceived by PWD compared to PWOD and the impact of any disparities identified on transition outcomes. Taking advantage of the large nationally representative contemporary cohort of Medicare beneficiaries enrolled over a decade in the MCBS, quantitative methods will begin by

PRINCIPAL INVESTIGATOR (LAST, FIRST, MIDDLE): [name]

exploring the associations of all covariates to ADL and IADL stage transitions over 1, 2- and 3-year periods. A series of multivariable regressions will be implemented in Aims 2, 3, and 4 to provide a comprehensive perspective on disparities and the factors influencing transitions. After quantifying the net contribution (if any) of each comparator to outcome transitions, we will then use parameter estimates generated by these analyses in the Aim 4 simulation study. The goal will be to simulate the maximum effect of alternative programs intended to improve access to care, quality of care, and the technical and other qualities of PCPs on the wellbeing of the US Medicare population.

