#### Addendum:

The comparators as used in this proposal address the magnitude of gaps across 5 healthcare quality dimensions as experienced by people at each of 4 stages of disability in comparison to those without disabilities, and the implications of those quality gaps to risks of functional deterioration. The health care quality dimensions as assessed by the patient include 1) Care coordination and quality, 2) Access barriers, 3) Technical skills of the PCP, 4) Interpersonal skills of the PCP, 5) Quality of information provided by the PCP.

PRINCIPAL INVESTIGATOR (LAST, FIRST, MIDDLE): [name]

---

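### Aim 2 reports and powers every stage contrast against stage I, itself a disabled group, so stages II, III and IV versus people without disabilities get no adjusted interval or test

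*Combined protocol and SAP*

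**What the plan says.** The target comparison is stated plainly. The quantitative overview in Project Plan and Timeline says "Our specific aims focus on empirically quantifying disparities in the quality of health and PCP care as perceived by PWD compared to PWOD". The Addendum is more specific: it describes quality gaps "as experienced by people at each of 4 stages of disability in comparison to those without disabilities".

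The Aim 2 paragraph of Data Analysis uses a different baseline. On the multinomial models of the trichotomous comparators, the text is: "We will report adjusted relative risk ratios (RRRs) and their 95% confidence intervals (CIs) for the ADL and IADL stages (stage I as reference"). The linear models of the continuous comparators are treated alike: "we will report sample weighted estimates for the ADL and IADL stages (stage I as reference) obtained through linear regression".

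The Sample size section follows the same choice: "The detectable RRRs comparing other stages to stage I are shown in Table 3". That table covers 0, II, III and IV, each versus I. Table 1 defines stage 0 as no difficulty and stage I as mild difficulty. No section gives a reason for taking stage I as the reference.

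**The concern.** Aim 2 exists to measure how far people with disabilities experience worse access and quality. With stage I as reference, three of the four reported contrasts (II, III and IV versus I) compare one disabled group with another. Only 0 versus I compares disabled with non-disabled people, and only at the mildest stage.

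A reader would therefore see no adjusted interval or test for the gap at the moderate, severe and complete stages, and Table 3 does not show that those gaps are detectable.

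Nor can the contrasts against stage I stand in for the missing ones. Whether they understate or overstate the gap depends on its shape across stages. The background section reports a non-monotone preliminary pattern for one service: "people with mild disabilities were more likely to receive influenza vaccines than PWOD", while the most severely disabled were less likely to be vaccinated. The direction cannot be assumed.

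**Working it through.** **1. Is the missing contrast planned elsewhere?** Three places come close, and none supplies it.
- The general approach in Data Analysis plans bi-variable associations, which are unadjusted.
- The Year 1 deliverables (Table 9) plan descriptive analyses by stage and comparator.
- The Year 3 deliverables compare people without disabilities with those at each stage, but within the Aim 4 simulations of transition outcomes, not for the Aim 2 comparator gaps.

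**2. How many people are affected?** Raw counts come from Table 5, captioned "Table 5. Sample size shown for 3 panels; expected size for 10 panels will be 40,000". The stage label II is printed twice; the second is read as III.
- ADL: (995 + 728 + 185) / (1,942 + 995 + 728 + 185) = 1,908 / 3,850 = 49.6%.
- IADL: (1,141 + 1,558 + 341) / (2,094 + 1,141 + 1,558 + 341) = 3,040 / 5,134 = 59.2%.

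**3. Can the intervals be recovered from the planned output?** The point estimate can: RRR(k vs 0) = RRR(k vs I) / RRR(0 vs I). The standard error cannot, because both terms share the stage I group.

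Inputs: Table 5 raw counts × 10/3, giving 27,360, 6,473, 3,317, 2,427 and 617 for ADL 0 to IV; stage I proportions 13.32% and 60.19% for categories 1 and 2 (Sample size), used in every stage; simple random sampling.

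Variance per stage on the log scale: v = (1/0.1332 + 1/0.6019)/n = 9.169/n. This gives v(0) = 0.000335, v(I) = 0.001416, v(II) = 0.002764, v(III) = 0.003778 and v(IV) = 0.014869.
- True SE, k vs 0: √(v(k) + v(0)).
- SE rebuilt by adding the two reported variances: √(v(k) + v(I) + v(0) + v(I)).

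| Stage | True SE vs 0 | Rebuilt SE | Ratio |
|---|---|---|---|
| II | 0.0557 | 0.0770 | 1.38 |
| III | 0.0641 | 0.0833 | 1.30 |
| IV | 0.1233 | 0.1343 | 1.09 |

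**4. Can the direction of distortion go either way?** These RRRs versus 0 for stages I to IV are assumed purely for illustration.
- 1.2, 1.4, 1.6, 2.0: II to IV would be reported as 1.4/1.2 = 1.17, 1.6/1.2 = 1.33 and 2.0/1.2 = 1.67, so understated.
- 0.85, 1.0, 1.2, 1.5: II to IV would be reported as 1.0/0.85 = 1.18, 1.2/0.85 = 1.41 and 1.5/0.85 = 1.76, so overstated.

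**5. Power.** First, Table 3 itself. The method is a Wald test on the log RRR with 80% power, two-sided 5%, no design effect and the variance taken under the alternative. The detectable RRR is exp[(1.960 + 0.842) × SE].

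| Category 1 vs 2, stage I reference | Table 3 | Recomputed |
|---|---|---|
| 0 vs I | 0.91 | 0.89 |
| II vs I | 1.15 | 1.19 |
| III vs I | 1.16 | 1.21 |
| IV vs I | 1.29 | 1.39 |

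Table 3 does not reproduce and the plan does not state its formula, so no before-and-after power comparison is made here.

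The same method with stage 0 as reference needs the stage 0 comparator distribution, which the documents do not give. It was varied from equal to stage I (13.32/60.19/26.49%) to RRRs of 0.7 and 1.3 versus stage I (8.97/57.90/33.13%). Detectable category 1 vs 2 RRRs versus 0:
- I: 1.12–1.14
- II: 1.16–1.19
- III: 1.19–1.22
- IV: 1.37–1.43

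A design effect would widen these. The Table 5 standard errors imply about 1.8 to 4.2 for the stage percentages. With an assumed 2.3, N = 40,000 and the stage 0 distribution varied only as far as RRRs of 0.80 and 1.20, the values are 1.25–1.28, 1.29–1.32 and 1.58–1.64 for II, III and IV.

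**The case against.** The strongest reply is that this is only a reparameterisation. Changing the reference level leaves the likelihood and fit unchanged, and the analyst can obtain any contrast versus stage 0, with its interval, from the same fitted model. That is true, and it means no estimate is biased and no information is lost. But the plan specifies what will be reported and powered, and the contrasts its own question asks for are not among them.

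A second reply is that stage I may suit the aim, in Importance of knowledge to be gained, of finding functional thresholds linked to disparities. The plan never gives this as a reason, and stage-to-stage contrasts stay available under a stage 0 reference.

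Third, power is little affected. This stands: at equal proportions the SE versus 0 is 0.86, 0.89 and 0.97 times the SE versus I for II, III and IV.

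Fourth, the inflation percentages describe what a reader would get wrong, and the RRRs in step 4 are invented. Both are fair. The first shows that the intervals cannot be rebuilt from the output, the second only that the direction is open.

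Fifth, stage 0 on one scale is not exactly the plan's non-disabled group, defined as "and PWOD as being at ADL- and IADL-0". At least (8,208 − 6,924)/8,208 = 15.6% of ADL-0 respondents (weighted: (69.25 − 59.65)/69.25 = 13.9%) have an IADL limitation. That definition sits under the qualitative selection criteria, so it supports a sensitivity analysis rather than a different main reference.

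Finally, a later protocol is scheduled and could settle the wording. That makes the change easy, but does not correct the present rule.

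**Conclusion.** The concern holds. The stated Aim 2 reference does not match the stated question: II, III and IV versus 0 have no planned adjusted interval, test or power figure, and these stages hold 49.6% (ADL) and 59.2% (IADL) of respondents with limitations. The fault lies in the choice of reported contrasts, not in the model. It should be fixed, but it does not threaten the data or the fit.

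The shares come straight from Table 5. The SE ratios rest on equal category distributions and simple random sampling. The detectable RRRs rest on an assumed stage 0 distribution and no design effect except where stated. No gain in power is claimed.

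**What to change.** Make stage 0 the reference in both Aim 2 models, multinomial and linear. Suggested wording:

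> We will report adjusted RRRs (or mean differences) with 95% CIs for ADL and IADL stages I, II, III and IV versus stage 0; stage-to-stage contrasts are secondary.

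Recompute Table 3 for I, II, III and IV versus 0, and state the formula, the assumed stage 0 comparator distribution and any design effect.

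As an optional sensitivity analysis, use people at stage 0 on both ADL and IADL as the reference.

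The cost is one reference-level setting in the code and a recomputed table. No new data are needed and the model fit does not change.

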#### **Preliminary findings:**

Our preliminary work established strong partnerships between stakeholders and scientists. The stakeholder and scientist teams contributed equally to this proposal, generating ideas, creating and finalizing the specific Aims, establishing the initial protocol, interpreting preliminary findings, running groups in Second Life, and establishing a shared timeline.

**Qualitative and CPBR:** The stakeholder and scientific teams had multiple group meetings in Second Life where they worked on protocol design, interpretation of the preliminary results, and all other project preparations. The PI and stakeholder consultant ([name] and [name]) ran 4 pilot peer support groups in VAI on the inaccessibility of medical equipment and

PRINCIPAL INVESTIGATOR (LAST, FIRST, MIDDLE): [name]

services (see example of de-identified “chat” in Appendix C). The “public abstract” was written iteratively partnering between the stakeholder and quantitative analytic teams. We reached our readability goal at or below the 6th grade level. Readability was estimated by the Flesch-Kincaid Grade Level score, which was approximately at grade 5.5 based on the USA educational system.

**Quantitative:** Using MCBS data from 3 panels active at the time of the Fall interview in 2005 (N=10,399) and with complete information, we applied a multinomial logistic regression model studying 1-year transition outcomes (2006 on the 4-level transition outcome with no change in function being reference). The global quality comparator was most consistently associated with outcome transition. Poorer perceived healthcare was significantly associated with 1-year, functional deterioration, institutionalization, and mortality (all p-values ≤0.03). Poorer perceived healthcare quality was strongly associated with functional improvement (p=.0001). Both functional improvement and deterioration were strongly associated with poorer access (both p<.0001). Perceptions of poorer access were also associated with death at 1 year (p=.02).

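### Aim 3 asks who is less likely to have a negative transition, but names only ratios to no change as model output, and these would overstate risk ratios under the pilot's pattern

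*Combined protocol and SAP*

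**What the plan says.** Under Data Analysis, Aim 3 is to determine whether people who rate their access, care and primary care provider well "will be less likely to experience a negative transition outcome". On the model it says: "The 5-state transition outcome will be modeled by multinomial logistic regression models with no change in function as reference". On output it says: "We will report RRRs and their 95% CIs". The relative risk of each state is then defined as its probability "divided by the probability of remaining at the same ADL stage". Aim 3 names no predicted probability, risk ratio or risk difference.

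The general approach, which covers every Aim, adds weighted summary statistics and unadjusted two-variable associations with outcome, in no stated form.

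The pilot, under Preliminary findings, used a "4-level transition outcome with no change in function being reference". It reports: "Both functional improvement and deterioration were strongly associated with poorer access (both p<.0001"). Overall perceived quality showed the same pattern: poorer ratings went with deterioration, institutionalization and death (all p-values at or below 0.03) and also with improvement (p=.0001). No RRRs or state probabilities are printed.

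Aim 4 uses coefficients from similar models to predict the prevalence of each state when a comparator is optimized, with confidence intervals, at 1, 2 and 3 years.

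**The concern.** Whether someone is less likely to die, enter an institution or deteriorate is a question about probability. An RRR answers a different one: how a state's probability compares with the probability of staying at the same stage. The two agree only if the no-change probability is the same at the comparator levels being compared.

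The pilot gives reason to doubt that. If poorer access goes with more improvement as well as more deterioration, both draw people out of the denominator, and a favourable outcome then helps to inflate the ratios for the unfavourable ones. A reader who takes these ratios as risks would see too large an effect. Omitting the improvement association from the surveillance tool, which the member-checking section contemplates, would not remove its effect on the other RRRs.

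**Working it through.** **Plan's own figure.** Table 4 gives the only Aim 3 numbers, "assuming 80% power and 5% significance level". For dissatisfied versus middle on comparator 1 (care coordination and quality), the detectable RRRs are death 1.71, institutionalization 2.71, deterioration 1.50 and improvement 1.49. They cannot be reproduced, because the reference transition probabilities behind them are not printed. The baselines below are therefore assumptions.

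**Identity.** At fixed covariates, with p0k the reference-group probability of state k and RRR = 1 for no change:

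RR_j = RRR_j / D, where D = sum over k of p0k × RRR_k.

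D is also the no-change probability in the reference group divided by that in the exposed group. If no change falls, D exceeds 1 and every RRR exceeds its risk ratio. An RRR between 1 and D has the opposite sign on the risk scale.

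**Size for deterioration.** Improvement RRR 1.49, deterioration RRR 1.50, death and institutionalization RRRs 1.00:

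| No change / improve / deteriorate / other | D | RR for deterioration = 1.50/D |
|---|---|---|
| .80 / .05 / .10 / .05 | .80 + .0745 + .15 + .05 = 1.075 | 1.40 |
| .72 / .08 / .14 / .06 | .72 + .1192 + .21 + .06 = 1.109 | 1.35 |
| .65 / .12 / .16 / .07 | .65 + .1788 + .24 + .07 = 1.139 | 1.32 |

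**Stage 0** cannot improve and is 69.25% of the weighted sample by ADL (Table 5). With assumed .85 / 0 / .11 / .01 / .03 (no change, improve, deteriorate, institution, death) and death and institutionalization RRRs of 1.10, D = .85 + .165 + .011 + .033 = 1.059, and 1.50 becomes 1.42. The overstatement is smaller there but present.

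**Can the sign reverse?** In the table above, the reversal window for death and institutionalization runs from an RRR of 1.00 to about 1.07-1.14. Compare it with the smallest significant RRR that Table 4 implies. With SE = ln(RRR)/2.80, the threshold is exp(1.96 × SE), which is the tabled RRR raised to the power 0.70:

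- Death: 1.71 gives about 1.46 (dissatisfied); 1.24 gives about 1.16 (satisfied).
- Institutionalization: 2.71 gives about 2.01 (dissatisfied); 1.63 gives about 1.41 (satisfied).

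All lie above 1.14, so at 1 year the window falls where the test would not be significant.

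A direct check used unadjusted Wald intervals and group sizes of 40,000 × 13.32% = 5,328 and 40,000 × 60.19% = 24,076. These shares are the stage I comparator 1 distribution, used as a proxy with no attrition.

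- *1 year, assumed:* no change falls from .70 to .62 and death stays at .045. The death RRR is .70/.62 = 1.13, CI 0.98-1.30. Not significant.
- *Longer follow-up, assumed:* no change falls from .50 to .40 and death stays at .11. The death RRR is .50/.40 = 1.25, CI 1.13-1.38 (1.08-1.44 with design effect 2). If death instead falls from .110 to .107 (RR 0.97), the RRR is 1.22, CI 1.10-1.35 (1.05-1.40 with design effect 2).

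A significant wrong-sign result therefore appeared only with a no-change baseline of about 50%, well below the 65-80% used for the size estimate.

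**Deterioration itself.** For improvement alone to reverse its sign, (RRR for improvement − 1) must exceed (RRR for deterioration − 1) by the factor (1 − p_det)/p_imp. That is .90/.06 = 15.0, .86/.10 = 8.6 or .80/.15 = 5.3 across three assumed baselines. Nothing in the pilot suggests such a gap.

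**The case against.** An RRR is a valid measure, and the plan defines its term in the sentence that uses it. That stands: the model is not wrong, and the gap lies between the measure and the question.

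Aim 4 puts every state on the probability scale with confidence intervals, so a marked discrepancy would surface there. This stands in part. Those predictions set everyone to the optimal level of a comparator in order to rank policies, and they are not tied to the Aim 3 conclusion. In Table 9, comparator effects are established in Year 3 month 6, papers on them are due in month 7, and simulation write-up begins in month 8. A later, undated item does join comparator effects with simulations.

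RRRs are also not the only planned output, since unadjusted associations are promised for every Aim. They do not replace an adjusted probability.

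Two stronger readings are tempting. One is that the pilot already shows reversed signs. It does not: it prints p-values without effect sizes, so it shows the condition for inflation and neither its size nor a reversal. The other is that stakeholders will be handed RRRs labelled as relative risks. The documents promise them tables, figures and simplified scenarios, without stating the measure.

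**Conclusion.** The point holds as a mismatch between question and reported measure. If poorer ratings raise both improvement and deterioration, Aim 3's RRRs will overstate risk ratios in the same direction. An apparent 50% excess in deterioration would be roughly 32-40% on the risk scale.

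That range is an illustration. It rests on assumed baselines (65-80% unchanged) and on Table 4's detectable RRRs for comparator 1 being treated as effects, including for access. The overstatement also depends on the no-change probability falling; if it rose, RRRs would understate risk.

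A reader might infer that Aim 3 is likely to declare harm where risk is unchanged or lower. The documents do not support that. Reversal is a theoretical possibility for small death or institutionalization RRRs, mainly at longer follow-up where no change is less common, and it is unlikely to be significant at 1 year. This is a worthwhile reporting improvement and no ground for replacing the model.

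**What to change.** Keep the multinomial models. From the same fits, add to Aim 3 the adjusted predicted probability of each of the five states at each comparator level, averaged over the sample, at 1, 2 and 3 years. Give survey-based confidence intervals for the differences between levels. State that the Aim 3 conclusion about negative transitions is drawn from these differences, with RRRs reported alongside. Replace the label relative risk, in Aim 3 and in the Sample size section, with relative risk ratio or ratio to no change.

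The cost is one post-estimation step and some extra table columns. No new data or models are needed, and Aim 4 already requires the same kind of prediction.
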